1.0 PROTOCOL SUMMARY AND/OR SCHEMA

Duration: 24 weeks

Background: Atrophic vaginitis is a significant complaint in 40% of postmenopausal women. While non-hormonal therapies are available for the treatment of many of the sequelae of menopause, estrogen has been shown to be the most effective treatment option for menopause induced urogenital atrophy. However, systemic estrogen has traditionally been contraindicated in women with breast cancer or other estrogen dependent cancers because it may stimulate any remaining microscopic foci of cancer or be a factor in the occurrence of a second primary. Therapies directed at reducing breast cancer risk usually act by blocking estrogen. In recent years, local vaginal estrogen with known minimal absorption has emerged as a possible treatment option for such patients. Anecdotal evidence suggests that breast cancer patients have positive experiences with vaginal 17- β estradiol, which is offered to them only after failing other local therapies such as lubricants.

Aromatase inhibitors (AI's) block the peripheral conversion of androgens to estrogen, resulting in sub-physiologic levels of estrogen that may lead to more profound urogenital atrophy. Original studies evaluating vaginal 17- β estradiol in postmenopausal women found only a transient increase in estradiol levels with return to baseline within 12 weeks. However, a recent report (n=6) performed by Kendall et al. demonstrated elevation in estradiol levels in 5 out of 6 women on aromatase inhibitors after two weeks of treatment with vaginal 17- β estradiol. After twelve weeks of therapy, estradiol levels decreased, but returned to pre-treatment levels in only 2 out of 6 women. The small sample size renders it difficult to reach definitive conclusions, but it does underscore the need to evaluate concurrent use of AI's and vaginal 17- β estradiol.

Study Objective:

The primary specific aim is to determine the change in estradiol and FSH from baseline to twelve weeks in postmenopausal women receiving adjuvant aromatase inhibitors during treatment with low dose vaginal 10 μ g 17- β estradiol. A secondary specific aim is to compare the rise in estradiol in women on letrozole vs. anastrozole during treatment with low dose vaginal 10 μ g 17- β estradiol to see if there are differences between aromatase inhibitors. Another secondary specific aim is to describe patterns of estradiol and FSH levels over the twenty-four week study period. A third secondary aim is to compare the patient's FSFI score at baseline, weeks 12 and 24.

Patient Population: 60 postmenopausal breast cancer patients who have completed their primary treatment for breast cancer with the exception of endocrine therapy who are currently being treated with adjuvant aromatase inhibitors with no evidence of disease. 60 women are being recruited with the goal of obtaining 48 evaluable patients.

Study Design: This study is a prospective longitudinal pilot study measuring serum estradiol and follicle stimulating hormone (FSH) levels in 60 postmenopausal breast cancer patients currently receiving treatment with adjuvant aromatase inhibitors (30 being treated with letrozole and 30 with anastrozole) who are initiated on vaginal estrogen for symptoms of urogenital atrophy. After a patient elects to participate and provides informed consent, a blood sample will be obtained to measure baseline estradiol and FSH levels. Patients will then receive a prescription

for vaginal 10 μ g 17- β estradiol. We hypothesize that low dose vaginal 17- β estradiol is a potentially safe and effective intervention, which does not cause an elevation in serum estradiol levels at 12 weeks in postmenopausal breast cancer patients on aromatase inhibitor therapy. In addition to studying the primary endpoint of estradiol levels, we will also study FSH, and FSFI/menopause symptom checklist as secondary endpoints.

All subjects will receive vaginal 10 μ g 17- β estradiol tablets. The primary endpoint will be change in estradiol and FSH from baseline to 12 weeks. Each subject will serve as their own control. Serum estradiol and follicle stimulating hormone (FSH) will be monitored closely from 0-24 weeks. Estradiol and FSH levels will be measured at baseline, and subsequently at weeks 2, 7, 12, 18 and 24 after commencing therapy with vaginal 10 μ g 17- β estradiol. The bloodwork will take less than one hour to perform and will be drawn +/-72 hours from the date the patient is due for bloodwork. Baseline bloodwork will be drawn within 14 days of study enrollment prior to the initiation of vaginal 10 μ g 17- β estradiol. Patients will be encouraged to come for their research bloodwork 12-24 hours after the insertion of the vaginal 10 μ g 17- β estradiol. Patients will record in their diary the time of their last vaginal 10 μ g 17- β estradiol tablet insertion. Along with the laboratory measurements of estradiol and FSH, the FSFI and a menopause symptom checklist will be administered at baseline, and the 12 and 24 week time points +/-72 hours. The baseline FSFI and menopause symptom checklist will be completed within 14 days of study enrollment prior to the initiation of vaginal 10 μ g 17- β estradiol. The FSFI will take approximately 10 minutes to complete and the menopause quality of life checklist questionnaire takes approximately 3 minutes to complete.

Both the patients and the investigators will be blinded to the results of the estradiol and FSH assays for the 24 weeks of study therapy. Results will be unblinded after accrual is complete and all patients have completed the 24 weeks of planned therapy. At week 24, patients can choose to remain on vaginal 10 μ g 17- β estradiol or discontinue the treatment. Patient's estradiol levels may continue to be monitored for the duration of their treatment with vaginal 10 μ g 17- β estradiol at her physician's discretion and depending on the findings of this study. We will continue to collect this data if the patient is being followed at MSKCC. Patients can choose to remain on it for as long as they desire.

2.0 OBJECTIVES AND SCIENTIFIC AIMS

SPECIFIC AIMS:

Primary Specific Aim:

- To determine the change in estradiol and FSH from baseline to twelve weeks in postmenopausal women receiving adjuvant aromatase inhibitors during treatment with low dose vaginal 10 μ g 17- β estradiol.

Secondary Specific Aims:

- To compare the rise in estradiol in women on letrozole vs. anastrozole during treatment with low dose vaginal 10 μ g 17- β estradiol to see if there are differences between aromatase inhibitors.
- To describe patterns of estradiol and FSH levels over the twenty-four week study period.

- To compare the patient's FSI scores and menopause quality of life questionnaire at baseline, week 12 and week 24

3.0 BACKGROUND AND RATIONALE

Many commonly used treatments for breast cancer, including adjuvant chemotherapy and endocrine therapy, either induce menopause or increase the frequency of urogenital complaints including vaginal dryness, irritation, pruritus, dyspareunia, urinary frequency and urinary incontinence. Aromatase inhibitors (AIs) are used to treat postmenopausal patients with both early stage and metastatic disease. AIs block the peripheral conversion of androgens to estrogen, resulting in sub-physiologic levels of estrogen that may lead to more profound urogenital atrophy. Estrogen has been shown to be the most effective agent for treatment of menopause induced urogenital atrophy. However, breast cancer patients are discouraged from using systemic estrogens because they may reduce the effectiveness of adjuvant hormonal therapy and may increase the risk of disease recurrence or new primaries. Hormone replacement therapy (HRT) has been shown to increase recurrence rates in patients with hormone sensitive breast cancer.¹ Vaginal creams or suppositories are considered and often given to these women with breast cancer, but the safety of topical estrogens in this population is unknown.

Low dose vaginal 17- β estradiol was shown to be highly effective in treating menopausal urogenital atrophy in women without cancer.² Vaginal 17- β estradiol was designed to relieve symptoms of urogenital hypoestrogenism with minimal systemic absorption and improved ease of usage compared to other vaginal estrogen formulations. In a study comparing 17- β estradiol to vaginal estrogen cream, both methods were equivalent for relief of atrophic vaginitis symptoms, but patients using vaginal 17- β estradiol had less systemic estrogen absorption, less endometrial proliferation and greater overall satisfaction.³ In another study, vaginal 17- β estradiol caused vaginal maturation, which gradually diminished absorption and systemic "spill over" of estradiol.⁴ In postmenopausal women after fourteen days of treatment, maturation of the vaginal epithelium occurred and absorption of estradiol subsequently declined significantly. FSH levels were unchanged during treatment with the 17- β estradiol. When systemic estradiol levels increase, FSH levels decrease correspondingly. Given the results of these studies, it was felt vaginal 17- β estradiol was efficacious and safe even for women trying to avoid estrogens. Recently a lower dose, 10 mcg 17- β estradiol, was FDA approved for postmenopausal women and is now readily available.

Despite the prevalence of urogenital symptoms in women with breast cancer, treatments have not been well studied in this population and are limited to over the counter lubricants, moisturizers, and dilator use with minimal impact. Vaginal 17- β estradiol was initially considered to be efficacious and safe even for women trying to avoid estrogens, and became widely prescribed to patients with breast cancer including women on endocrine therapy. Studies evaluating vaginal 17- β estradiol in postmenopausal women without breast cancer found only a transient increase in estradiol levels with return to baseline within twelve weeks. However, a recent prospective small observational study (n=6) performed by Kendall et al. demonstrated elevation in estradiol levels in 5 out of 6 women on aromatase inhibitors after two weeks of treatment with 25 mcg 17- β estradiol.⁵ After twelve weeks of therapy, estradiol levels decreased, but returned to pre-treatment levels in only 2 out of 6 women, which calls into question the safety of low dose 17- β estradiol in women with breast cancer. . The concern is that using low-dose vaginal estrogens

may negate or diminish the effect of AIs. However, the small sample size renders it difficult to reach definitive conclusions, but it does underscore the need to perform a rigorous, adequately sized clinical trial to evaluate concurrent use of aromatase inhibitors and low dose 17- β estradiol. While it is clear that lowering estradiol levels as much as possible is ideal in preventing recurrences, the absolute estradiol level to minimize risk is unknown.

While the study suggests that this transient increase in estradiol may be of concern in this population, there is no clear evidence that a transient rise in estradiol causes any detrimental effects in patients with breast cancer. How much, if any, of these topical estrogens are absorbed through the mucous membranes of the vagina into the circulation is not known and the impact of low dose estradiol absorption on breast cancer outcomes is also unknown. Furthermore, the absorption will wane as the mucus membranes regenerate under estrogen exposure, which explains the return to baseline after 12 weeks noted in general population studies. In addition, since the vaginal mucosa of women using AI's has been even more depleted of estrogen exposure, it intuitively makes sense that a return to baseline will take longer. Therefore, this study will follow women for 24 weeks to see if longer therapy impacts estradiol level and systemic absorption. Finally, it is not known if the absorption of 17- β estradiol is different in the breast cancer population. It is therefore critical that we obtain further information regarding the safety of 17- β estradiol, an apparently efficacious treatment, in patients with breast cancer being treated with AIs. Since the risk/benefit of 17- β estradiol has not been rigorously evaluated and the lower 10mcg is now available, it was felt that evaluating the lowest possible dose for efficacy is the logical first step. We hypothesize that the systemic absorption of estrogen might be less with the 10mcg 17- β estradiol than with the 25mcg 17- β estradiol.

The third generation AIs (anastrozole, letrozole, exemestane, vorozole) are the most potent and specific AIs, leading to improved tolerability and efficacy compared to prior generation AIs⁶. However, there appears to be some variation between the third generation AIs. Clinical data shows that letrozole more effectively suppresses all plasma estrogen fractions, including estradiol, when compared to anastrozole. Geisler et al. showed that with respect to both tissue estrogen and plasma estrogen, letrozole consistently suppressed the estradiol level below the levels recorded for anastrozole⁷. The average percentage of suppression for plasma estradiol during treatment with letrozole was 95.2% vs 92.8% with anastrozole, which was statistically significant with a p=0.018. However, in an open randomized trial of second line endocrine therapy in patients with advanced breast cancer, there was no statistically significant difference in the median time to progression in patients treated with letrozole vs anastrozole⁸. Although letrozole did have a statistically significant superior overall response rate 19.1% vs 12.3% with anastrozole with a p=0.013. Therefore, this study will also compare changes in serum estradiol levels in women with breast cancer being treated with letrozole vs anastrozole during treatment with vaginal 17- β estradiol. It is unclear if it will take a longer time for estradiol levels to normalize in patients on letrozole given the more effective suppression. Patients who are currently on exemestane will be excluded from this study because metabolites of exemestane interfere with the estradiol assay causing elevations in estradiol measurements.

AIs are a commonly used endocrine therapy that causes vaginal dryness.⁶ One component of sexual functioning, vaginal dryness, is an important predictor of sexual health in this population.⁹ Sexual dysfunction is a side effect of both chemotherapy and endocrine therapies, causing a

substantial burden on women with breast cancer.¹⁰⁻¹¹ Sexual functioning affects quality of life in women during their treatment and survivorship.¹² The Female Sexual Function Index (FSFI) is a validated instrument, which is an overall measure of female sexual dysfunction.¹³ It is based on six domains: desire, arousal, lubrication, orgasm, satisfaction and pain. In the study demonstrating validity and reliability of the FSFI, an analysis of sensitivity and specificity yielded a cut score of 26.55 for the identification of women with sexual dysfunction¹⁴ Therefore, we will report the prevalence of sexual dysfunction in this population as the percentage of women with FSFI scores less than or equal to 26.

The menopause SCL checklist is an instrument devised by the National Surgical Adjuvant Breast Project for the use in the P-1 and P-2 breast cancer chemoprevention trials.¹⁵ It contains 36 items querying a range of physical and psychological symptoms, as well as symptoms associated with estrogen deprivation. This instrument was successfully administered as part of a baseline QOL assessment to over 9700 participants in the NSABP P1 trial. Estrogen levels may influence mood and quality of life. It takes approximately 3 minutes to complete.

Atrophic vaginitis in breast cancer survivors is prevalent and its management is complex. It is therefore critical that we obtain further information regarding the safety of 17- β estradiol, an apparently efficacious treatment, in patients with breast cancer treated with AIs. This pilot intervention study of 10 μ g 17- β estradiol will inform future investigations. A 10 μ g 17- β estradiol tablet was recently FDA approved and is now commercially available. The 10mcg vaginal 17- β estradiol dose has never been studied in women with breast cancer. This will be the first study evaluating 10mcg vaginal 17- β estradiol in women with breast cancer. In postmenopausal women without breast cancer, a randomized controlled trial was performed comparing the efficacy of 25mcg vaginal 17- β estradiol vs. 10mcg vaginal 17- β estradiol vs. placebo.¹⁶ Both the 10mcg and 25mcg vaginal 17- β estradiol were effective in the treatment of atrophic vaginitis. However, there was greater improvement and relief of vaginal symptoms and more systemic absorption with the 25mcg vaginal 17- β estradiol. Depending on the results from this study, our next study may be a randomized trial evaluating the 10 μ g vs 25 μ g dose of vaginal 17- β estradiol.

4.0 OVERVIEW OF STUDY DESIGN/INTERVENTION

4.1 Design

This study is a prospective longitudinal pilot study measuring serum estradiol levels in 60 breast cancer patients in order to obtain 48 evaluable patients currently receiving treatments with adjuvant aromatase inhibitors. The goal is to have 30 patients on letrozole and 30 on anastrozole who are initiated on vaginal estrogen for symptoms of urogenital atrophy. Eligible women (see eligibility criteria section 6.0) seen in either breast medicine or gynecology clinic at MSKCC will be counseled on the use of low dose vaginal estrogens for symptomatic relief. A member of the clinical research staff will invite patients interested in using vaginal estrogens to participate in the study. After a patient elects to participate and provides informed consent, we will obtain serum to measure baseline estradiol and follicle stimulating hormone (FSH) levels. Patients will also complete the FSFI questionnaire. Patients will then receive a prescription for 10mcg vaginal 17- β estradiol.

All subjects will receive 10mcg vaginal 17-β estradiol tablets. The primary endpoint will be change in estradiol and FSH from baseline to 12 weeks. Each subject will serve as her own control. We will monitor serum estradiol and follicle stimulating hormone (FSH) levels closely from 0-24 weeks. We will measure serum estradiol and FSH levels at baseline, and subsequently at weeks 2, 7, 12, 18 and 24 after commencing therapy with 10mcg vaginal 17-β estradiol. The bloodwork will take less than one hour to perform and will be drawn +/- 72hrs from the date the patient is due for bloodwork. Baseline bloodwork will be drawn within 14 days of study enrollment prior to the initiation of vaginal 10 µg 17- β estradiol. Patients will be encouraged to come for their research bloodwork 12-24 hours after the insertion of the vaginal 10 µg 17- β estradiol tablets. Patients will record in their diary the time of their last vaginal 10 µg 17- β estradiol tablet insertion. Since we do not know the clinical significance of transient estradiol elevation in these patients, both the patients and the investigators will be blinded to the results of these assays for the 24 weeks of study therapy. This will also help avoid patient and investigator bias. Results will be unblinded after accrual is complete and all patients have completed the 24 weeks of planned therapy. At week 24, all patients go off study, but patients can choose to remain on vaginal 17-β estradiol or discontinue the treatment. Patient's estradiol levels may continue to be monitored for the duration of her treatment with vaginal 17-β estradiol at her physician's discretion and depending on the findings of this study. We will continue to collect this data if the patient is being followed at MSKCC. Patients can choose to remain on it for as long as they desire.

Use of conventional estradiol assays is not appropriate in this patient group due to inaccuracies in measuring serum estradiol levels <25 pmol/l. Therefore, serum estradiol levels will be measured using a more sensitive radioimmunoassay, which can accurately quantify the low levels of estradiol seen in postmenopausal women being treated with aromatase inhibitors. The assay will be done by a commercially available RIA kit from Diagnostic Systems Laboratories (Beckman Coulter Company). This test is specifically formulated as an Ultra-Sensitive estradiol assay. The assay measures estradiol in pg/ml and the assay sensitivity is 2.2 pg/ml. We will run the estradiol assays in batch mode depending on the accrual rate for the specimens. Assaying serial specimens in the same run will eliminate inter-assay variation. Specimen degradation and freeze thawing are not a problem since estradiol is a steroid hormone and extremely stable in serum/plasma.

The FSFI (Female Sexual Function Index) is an overall measure of sexual function and is based on six domains: desire, arousal, lubrication, orgasm, satisfaction and pain.¹³ The menopause SCL checklist is an instrument devised by the National Surgical Adjuvant Breast Project, which contains 36 items querying a range of physical and psychological symptoms, as well as symptoms associated with estrogen deprivation. We will administer the FSFI survey questionnaire and menopause symptom checklist via either paper or wireless tablet computers in private areas of waiting rooms at the MSKCC 64th street Breast Center and gyn 53rd street clinic at baseline, week 12 and week 24 +/-72hrs from the date the patient is due for the FSFI questionnaire and menopause symptom checklist. The FSFI will take approximately 10 minutes to complete and the menopause symptom

checklist takes approximately 3 minutes to complete. The paper or computers will be brought to enrolled patients by the study RSA at the designated visit dates (baseline, week 12, week 24) +/-72hrs. The baseline FSFI/menopause symptom checklist will be completed within 14 days of study enrollment prior to the initiation of vaginal 10 µg 17-β estradiol. Each patient will have a unique, secure username and password for entering information into the online survey. The computers, survey, and online security will be overseen by the MSKCC institutional Web Survey Core, which is under the direction of [name], who is an investigator on this protocol. The survey platform and Web Core server configuration have previously undergone MSKCC security and privacy review and approval, and the data will be stored on a secure server at the MSKCC New Jersey Data Center with capability for data transfer to CRDB. The survey will be programmed and maintained by [name], Senior Programmer for the Web Survey Core. The MSKCC Web Survey Core was developed for protocols like this one, which require secure, private administration of surveys, which are ideally administered electronically.

If a patient discontinues vaginal 17-β estradiol, we will gather information regarding her reason(s) for discontinuation and we will record this information in the medical record. If a patient fails to return for assessment during the defined intervals, one of the investigators will contact her and gather information regarding her reason(s) for not returning. If she is still using vaginal 17-β estradiol, we will ask her to return to have her estradiol level checked.

If at any time a patient develops recurrent disease (e.g. a new breast primary, locoregional recurrence, or distant recurrence) she will be taken off study and referred for alternative therapy. If a study participant develops recurrent disease while on Vagifem, a social worker will be available at the MSKCC breast medicine outpatient facility to debrief the patient. Should a patient develop unacceptable toxicity, defined as any Vagifem related toxicity greater than or equal to a grade three toxicity, she will also be removed from the study.

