4.2 Intervention

All study participants will receive 10mcg 17-β estradiol tablets. At the initial medicine or gynecology visit, we will instruct each patient to insert one 10mcg 17-β estradiol tablet into her vagina at bedtime for two weeks as the initiation dose. After the initial two-week period ends, the dosing will decrease to one tablet vaginally two times per week for the subsequent 22 weeks for maintenance. A member of the clinical research staff will explain the proper method of treatment administration using a standardized script. Patients can also refer to the package insert during the initial visit for further clarification. Patients will also be asked to keep a medication diary. In it they will record the date and time each estrogen tablet is used. They will also record any symptoms or side effects they experience. They will be required to bring completed diaries to their appointments.

Timepoints for FSH and estradiol bloodwork and FSFI survey:

Weeks	FSH	Estradiol	FSFI/Menopause Symptom Checklist
0	X	X	X
2	X	X	
7	X	X	
12	X	X	X
18	X	X	
24	X	X	X

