12.0 CRITERIA FOR THERAPEUTIC RESPONSE/OUTCOME ASSESSMENT

Primary Specific Aim:

- To determine the change in estradiol and FSH from baseline to twelve weeks in postmenopausal women receiving adjuvant aromatase inhibitors during treatment with low dose vaginal 10 μ g 17- β estradiol.

Secondary Specific Aims:

- To compare the rise in estradiol in women on letrozole vs. anastrozole during treatment with low dose vaginal 10 μ g 17- β estradiol to see if there are differences between aromatase inhibitors.
- To describe patterns of estradiol and FSH levels over the twenty-four week study period.
- To compare the patient's FSFI scores at baseline, week 12 and week 24

Both FSH and estradiol levels will be measured in the clinical chemistry laboratory at MSKCC. Conventional FSH assays will be used. However, use of conventional estradiol assays is not appropriate due to inaccuracies in measuring serum estradiol levels <25 pmol/l.

The study will be called “VAG” with a unique five digit identification number for each patient (for example VAG-123456). The specimens will be anonymized and no name will be needed. Each time a specimen is received for an individual, the same identifier (for example VAG-12345) will be used. The first digit after VAG will indicate the site where the subject was consented. (1 for Gynecology at 53rd Street, 2 for Breast at 66th Street, 3 for Commack, 4 for Basking Ridge, 5 for Rockville Center, 6 for Sleepy Hollow.) Only the date and comment (for example - baseline, 2 weeks, 7 weeks, etc) will be specific for the time relative to treatment. The specimen will be sent to the lab with a paper requisition since the panel will not be ordered in OMS. The specimens will be accessioned, aliquoted, tested and the results will be available on the hospital computer that is not accessible to the clinicians running the study (results are blinded).

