14.0 BIOSTATISTICS

This is a prospective longitudinal pilot study, and the targeted patient population is postmenopausal women with breast cancer being treated with adjuvant aromatase inhibitors who are initiated on vaginal 17 β -estradiol to relieve symptoms of atrophic vaginitis. These women have completed primary breast cancer treatment including surgery, radiation therapy, and chemotherapy with the exception of hormonal therapy and should have no evidence of disease. . One common symptom of breast cancer therapy is atrophic vaginitis. Recent literature has suggested that women with breast cancer who use estradiol vaginal tablets for the treatment of atrophic vaginitis have had spikes in serum estradiol. This is a potentially dangerous suggestion since breast tumors are often fueled by hormones. The published studies are observational and based on very small series of patients. The aim of this study is to prospectively evaluate this trend in a larger series of breast cancer patients who use vaginal estradiol tablets.

Serum estradiol levels and FSH levels will be assessed at baseline, and weeks 2, 7, 12, 18 and 24 during treatment with vaginal estradiol tablets. The bloodwork will take less than one hour to perform and will be drawn +/- 72hrs from the date the patient is due for bloodwork. Baseline bloodwork will be drawn within 14 days of study enrollment prior to the initiation of vaginal 10 μ g 17- β estradiol. Patients will be encouraged to come for their research bloodwork 12-24 hours after the insertion of the vaginal 10 μ g 17- β estradiol tablets. Patients will record in their diary the time of their last vaginal 10 μ g 17- β estradiol tablet insertion. FSFI (Female Sexual Function Index) is an overall measure of sexual function and is based on six domains: desire, arousal, lubrication, orgasm, satisfaction and pain.¹³ Along with the laboratory measurements of estradiol and FSH, the FSFI survey questionnaire and menopause symptom checklist will be administered at baseline, and the 12 and 24 week time points. The FSFI will take ten minutes and the menopause symptom checklist will take three minutes to complete. Both will be administered +/- 72hrs from the date the patient is due for the survey. The baseline FSFI and the menopause symptom checklist will be completed within 14 days of study enrollment prior to the initiation of vaginal 10 μ g 17- β estradiol.

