The primary analysis will focus on analyzing the change in estradiol level from baseline to 12 weeks using a two-sided paired t-test. We plan to recruit sixty eligible women, with the expectation that 48 (80%) will complete the study and be compliant. We plan to recruit 30 women who have been on anastrozole therapy and 30 women who have been on letrozole therapy. Patients who drop out due to self-withdrawal, recurrence or noncompliance will be eliminated from the primary analysis but will be examined closely. Patients are evaluable if they have at least baseline and week 12 values.

The primary analysis will be a two-sided paired t-test to evaluate whether there was a change in estradiol levels from baseline to 12 weeks. For a sample size of 48, we will be able to detect a difference of .41 or higher on a standard unit scale with 80% power and **5% type I error** using a paired t-test. To translate this into the scale commonly used to report estradiol, we examine a series of 6 breast cancer patients published by Kendall et al (2006). In Kendall et al, estradiol levels ranged from close to 0 to 5 pmol/l before starting vaginal estradiol, to close to 0 to 25 at 7 weeks. Based on these data, we conservatively estimate the standard deviation of the difference to be 7 (**roughly, range/4**). Thus, for a sample size of 48 we will be able to detect an absolute difference in estradiol of 2.88 pmol/l with 80% power and **5% type I error**.

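### The week-12 estradiol test pools blood draws from any point in the twice-weekly tablet cycle, because the 12-24 h draw is only encouraged and time since insertion has no role in the analysis

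*Combined protocol and SAP*

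**What the plan says.** All references are to the combined protocol and SAP.

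- **Target draw time.** Sections 1.0, 4.1, 10.0 and 14.0 each give the same soft instruction: "Patients will be encouraged to come for their research bloodwork 12-24 hours after the insertion". None makes it a requirement.
- **Firm rule.** Section 4.1 states that blood "will be drawn +/- 72hrs from the date the patient is due for bloodwork". It sets no limit on hours since the last tablet.
- **Dosing at week 12.** After two weeks of nightly use, Section 4.2 says "the dosing will decrease to one tablet vaginally two times per week for the subsequent 22 weeks for maintenance".
- **What is recorded.** Section 14.0: "Patients will record in their diary the time of their last vaginal" tablet insertion. For specimens, Section 12.0 says: "Only the date and comment (for example - baseline, 2 weeks, 7 weeks, etc) will be specific for the time relative to treatment". No clock time of draw is mentioned.
- **Analysis.** Section 14.0: "The primary analysis will be a two-sided paired t-test to evaluate whether there was a change in estradiol levels from baseline to 12 weeks". A woman is evaluable if she has baseline and week-12 values, with no condition on draw timing. Noncompliance is a reason for exclusion but is neither defined nor tied to draw timing. The ANCOVA sentence leaves its covariate list open and names only the type of aromatase inhibitor. No analysis by time since insertion is listed.
- **Hypothesis.** Section 1.0 expects a treatment "which does not cause an elevation in serum estradiol levels at 12 weeks".

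**The concern.** The sponsor states the 12-24 h target four times and collects insertion times, so it evidently regards timing as relevant to the measurement. Yet the plan neither schedules draws to that target nor analyses departures from it. At week 12, a value taken 18 h after a tablet and one taken about 90 h after count equally.

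This is a safety-motivated study whose Section 1.0 hypothesis is the absence of a rise. If the increment wanes between tablets, late draws shrink the measured rise and make a null result easier to obtain. A reader of a null week-12 result could not tell little absorption from late sampling.

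**Working it through.** **1. The plan's own figure.** Inputs from Section 14.0: n=48, SD of the paired difference 7 pmol/l, two-sided 5%, detectable difference 2.88 pmol/l (0.41 SD). Noncentral-t power with 47 degrees of freedom and noncentrality (2.88/7) × √48 is 79.7%. Solving for exactly 80% gives 0.413 SD, or 2.89 pmol/l. The figure reproduces.

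**2. How narrow the target is.** It is 12 h wide. That is 12/72 = 16.7% of a three-day tablet interval and 12/96 = 12.5% of a four-day one. The visit window is 2 × 72 = 144 h, longer than either interval, so a draw at any point in the cycle can be valid.

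**3. Illustration with exponential decay.** The documents give no time course after a tablet and no expected share of in-window draws. Assumptions: a true rise of 2.88 pmol/l at 18 h, and an increment that decays with half-life h of 12, 24 or 36 h. The fraction retained at time t is g(t) = 2^(−(t−18)/h). With tablets alternately 3 and 4 days apart, one draw time per day over a week gives 18, 42, 66, 18, 42, 66 and 90 h. The five late times have mean retained fraction r. At h=12, r = (0.25 + 0.0625 + 0.25 + 0.0625 + 0.0156)/5 = 0.128.

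If a share f is in window, the mean rise is 2.88 × [f + (1−f)r]. Power is for n=48 with SD held at 7.

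| Half-life | r | f=85%: rise, power | f=70%: rise, power | Draw day unrelated to tablet day (f=2/7): rise, power |
|---|---|---|---|---|
| 12 h | 0.128 | 2.50, 68% | 2.13, 54% | 1.09, 18% |
| 24 h | 0.325 | 2.59, 71% | 2.30, 61% | 1.49, 30% |
| 36 h | 0.461 | 2.65, 73% | 2.41, 65% | 1.77, 40% |

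**4. The same question without a half-life.** Let late draws keep a fixed fraction r of the rise, and add the mixing variance: SD² = 49 + f(1−f)[2.88(1−r)]².

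- f=0.8, r=0.75: rise 2.74, power 75%
- f=0.8, r=0.5: rise 2.59, power 71%
- f=0.5, r=0.5: rise 2.16, power 55%
- f=0.5, r=0: rise 1.44, power 28%

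**5. The opposite direction.** Sections 4.2 and 9.0 have the tablet inserted at bedtime. With an assumed 22:00 insertion, a draw before 10:00 the next morning is earlier than 12 h. Under the same decay model, a 10 h draw reads 2^(8/36) = 1.17 to 2^(8/12) = 1.59 times the 18 h rise. Steps 3 and 4 leave such draws out.

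**6. What restriction to in-window women recovers.** At an effect of 2.88/7, with n = 48f:

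| In-window share | n | Power, subset | Power, pooled |
|---|---|---|---|
| 85% | 41 | 73% | 68-73% |
| 70% | 34 | 64% | 54-65% |
| 2/7 | 14 | 30% | 18-40% |

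The subset removes the dilution but recovers little power.

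**The case against.** **Direction.** A reader might infer that the plan biases the primary result toward no elevation. The documents do not support that as a certainty. They give no post-tablet time course, and early-morning draws after a bedtime tablet are allowed and could read high. Nor does dilution serve every stated hypothesis: Section 14.0 also expects estradiol to climb until about week 12, and dilution works against that. This objection stands. What remains is conditional: late draws dilute if the increment declines.

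**Size.** A reader might take 18-40% as the study's real power. That case assumes an instruction given in four sections has no effect, although a patient diary, instructions and calendar are listed as appendices. It is an extreme. Every figure also treats 2.88 pmol/l as an 18 h rise, whereas Section 14.0 derives it from an SD without fixing a draw time. This stands too, and the figures are illustrations only.

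**Silence.** The ANCOVA covariate list is open-ended and repeated-measures models are planned, so timing could be added later. That is true, but a covariate chosen after unblinding is a weaker safeguard than one prespecified. The primary t-test and the evaluability rule would still ignore timing.

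**Data already in hand.** A reader might suppose that hours since insertion are already recorded. Only the insertion time clearly is. With just a date and nominal week mentioned for the specimen, the interval may not be computable.

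**Conclusion.** The point holds in conditional form. The 12-24 h draw is encouraged and not required, the visit window exceeds a full maintenance tablet interval, and no planned analysis uses time since insertion. The week-12 test therefore pools draws from across the cycle. If the increment declines between tablets, late draws pull the result toward no elevation. With early draws also possible, net direction and size cannot be determined from the documents.

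Under the assumed 12-36 h half-lives, and with no early draws, the loss is about 7-12 points of power if 85% of draws are in window and about 15-26 points if 70% are. The primary result remains computable, but a null finding would be hard to interpret. The change should be made.

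**What to change.** No change to dosing is needed.

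1. **Scheduling (Sections 4.1, 10.0 and 14.0).** Book each maintenance-phase draw, within the existing window of 72 h either side of the due date, for 12-24 h after one of the woman's own scheduled tablets. The 144 h window exceeds the longest interval of 96 h, so it spans at least one tablet cycle. Keep women drawn outside 12-24 h evaluable, so that the expected 48 of 60 is not eroded.
2. **Data (Section 12.0).** Record the clock time of every draw, so that hours since insertion can be computed with the diary.
3. **Analysis (Section 14.0).** Keep the primary paired t-test and prespecify two sensitivity analyses.
   - Model post-baseline change on hours since last tablet using the twice-weekly phase only (weeks 7, 12, 18 and 24), and report the week-12 change at a fixed time inside the window, such as 18 h. Baseline is left out of the covariate because hours since last tablet is undefined before treatment. Week 2 is left out because it closes nightly dosing, where timing is confounded with dosing phase.
   - Repeat the primary test in women whose week-12 draw fell at 12-24 h. Label it supportive, because n is smaller and the subset is selected on behaviour after baseline.

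The cost is slightly less scheduling flexibility, one more recorded field and some added text. The in-window subset recovers little power, so the main gain comes from scheduling.
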